Since the inclusion of NHS24 as a Level 1 DBI provider in May 2020, it has become the main referral agency. We will select the comparator group from those accessing NHS24 who were not referred to DBI because they accessed services prior to its roll out throughout Scotland via NHS24. We will request Unscheduled Care Datamart (UCD) records, which links data from NHS24, Scottish Ambulance Service, Out of Hours Primary Care, Emergency Department, Acute and Mental Health services and deaths, for 2018-2019 for people who contacted NHS 24 in October 2019 to March 2020 for mental health reasons. The NHS24 data indicates whether a call went to the Mental Health Hub (MHH). NHS24 receives around 130,000 calls a month and around 3% of these are related to mental health₃₄. We will use a call related to mental health as the comparator event and collect information on service use outcomes in the year before and the year after the index call. The comparator event(s) is/are a good proxy for presenting to unscheduled care experiencing mental distress as measured by the distress thermometer used by Level 1 services to assess for referral to DBI. People who received DBI intervention during the same period will be identified through the DBI database held by Public Health Scotland which will be linked to the UCD by eDRIS.

We will also collect demographic information on these individuals e.g. age, gender, ethnicity, SIMD, geographic region, rates of previous unscheduled care use and presence of physical co-morbidity. We will use doubly robust estimation which combines a regression model of the outcome with a model for the exposure (ie the propensity score) to estimate the effect of an exposure on an outcome₃₅.

The use of unscheduled care in the year before and after the selected year for the comparator group and the data collection year for DBI service users will be compared to assess whether use of unscheduled care in the year after is lower for DBI service users. We will also collect data on the primary and (where available) secondary presenting problems as described by each unscheduled care service on the UCD for comparison. The presenting problem descriptors differ across the services. Where listed our analysis will include, but not be limited to:

- Mental health problems
- Self-harm

- Attempted suicide
- And completed suicide

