7 SAMPLE AND RECRUITMENT

7.1 Eligibility Criteria

The inclusion criteria for all study participants and the comparator groups are as follows:

DBI L2 individual quantitative surveys:

• All individuals accessing DBI in the first data collection year at participating DBI provider sites aged 16 years or over will be invited to participate.

DBI L2 service user qualitative interviews:

- Aged 16 years or over
- Agreed to be contacted for interview
- DBI service users who have experienced self-harm, suicidal thoughts or behaviour
- Referred to and received at least one supportive contact from a participating DBI L2 service
- Reported thoughts or acts of self-harm and/or suicide at any time within the past 12 months
- Level of literacy that allows informed consent, complete written records in English and participate in interviews

Comparator group:

- Those accessing NHS24 who were not referred to DBI because they accessed services prior to the roll out of DBI throughout Scotland via NHS24.
- People who contacted NHS 24 in October 2019 to March 2020 for mental health reasons.

NHS24 Comparator group interviews:

• Individuals who accessed NHS24 Mental Health Hub between Oct 2019 and March 2020.

DBI staff focus groups:

- DBI L2 staff members
- DBI Level 1 service representatives (police, ambulance and A&E)
- DBI local provider management
- DBI Central team leadership and DBI Programme Board members.

GP survey:

• GPs currently operating in Scotland with L1 DBI training.

The exclusion criteria are as follows:

DBI L2 individual surveys:

- DBI service users under the age of 16
- DBI service users for whom participation in the study is not deemed appropriate by DBI staff depending on individual circumstances

DBI service users qualitative interviews:

- DBI L2 service users who have responded to the quantitative survey but have not experienced self-harm, suicidal thoughts or behaviour
- Medically unfit for interview
- Unable to provide informed consent

- A level of literacy that is not sufficient to complete relevant assessment measures, engage with telephone contact and support or participate in interviews and/or are unable to provide contact details.
- Assessed to be at high or imminent risk of suicide before interview

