7.2 Sampling

7.2.1 Size of sample and rationale

L2 DBI service users survey sample: maximum 2,700 (some attrition is expected as data collection progresses, n=2,700 for 1st and n=1350 for 2nd DBI surveys, n=675 for 3-4 month follow-up survey, n=330 for 1 year survey). DBI referral numbers suggest that each DBI provider will receive 1000 referrals in 1 year. In the original evaluation, participants were recruited in a similar way with just under half (46%) completing the first survey. For the L2 DBI individual survey in this study participant sample numbers are based on responses gained in the original DBI evaluation including likely attrition rates for follow-up surveys.

L2 DBI qualitative interviews: maximum 75 (some attrition is expected as data collection progresses). Over the course of the 12-month recruitment period an estimated 6000 individuals will be referred to the six participating DBI L2 services. DBI Programme routine data indicates that 45% of referrals to DBI L2 services experience suicidal thoughts, behaviour or self-harm. This suggests that 2700 referrals are potentially eligible for in-depth qualitative interviews. Our target sample size for in-depth qualitative interviews is 75 (3%) and is achievable with well-trained project staff and a £25 gift as compensation for the time to participate in the interviews.

Comparator group quantitative analysis: 2500. The comparator group of those accessing NHS24 who were not referred to DBI because they accessed services prior to the roll out of DBI throughout Scotland via NHS24 (since the inclusion of NHS24 as a L1 DBI provider in May 2020 it has become the main referral agency) will be selected from the Unscheduled Care Datamart. We will request Unscheduled Care Datamart records for 2018-2019 for people who contacted NHS 24 in October 2019 to March 2020 for mental health reasons.

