For the comparator group quantitative analysis the sample size is based on 2500 people accessing the DBI L2 during the study period. Assuming the model: generalised linear model using binomial family and a logit link with dependent variable 'UCD use in the year after' and independent variables 'UCD use in the preceding year' and 'group' (DBI versus comparator). Estimating the following odds ratios for the model: intercept 0.80, group 0.70, UCD use in preceding year 2.0 and assuming the DBI group represents 10% of the total analysis sample and that the probability of UCD use in the preceding year is about 70% (estimate based on evaluation data) with alpha set to 0.05 we would have over 90% power to test that the odds ratio for 'group' is different to 1.

NHS 24 MHH qualitative interviews: 15. The sample of 15 interviews is based on the premise that the open invitation to participate through mental health lived experience networks will yield small numbers, however 15 interviews should be sufficient to provide the insights required for this study.

Stakeholder focus groups: 42 – 56 (6-8 per focus group). It is intended to hold one focus group per site. Given the relatively standardised nature of DBI it will not be necessary to hold multiple focus groups per site. 6-8 participants is a standard and recommended amount of people per focus group to aid discussion.

GP survey: 20. This should be sufficient to enable the generation of stylised pathways that are reflective of current practice. Recruitment of GPs to studies is very difficult due to their limited time so we would not wish to unnecessarily invite higher numbers to participate to minimise burden.

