The data linkage of the DBI L2 individual survey dataset and DBI routine dataset will be facilitated by ScotCen supported by [name] who is responsible for managing the DBI routine datasets in Public Health Scotland. ScotCen will securely transfer the survey dataset via Secure File Transfer Protocol with the unique identifier to eDRIS to enable them to link the survey data to the DBI routine dataset. The linked dataset will be held in the secure Safe Haven for the study team to access remotely. The linked dataset will be securely deleted 2 years following the study. This combined dataset will also be linked to the UCD by eDRIS. eDRIS will also be requested to link Unscheduled Care Datamart records for 2018-2019 for people who contacted NHS 24 in October 2019 to March 2020 for mental health reasons. [name] (Associate Medical Director NHS 24) will facilitate access to NHS24 data to identify individual patient records for the comparator group analysis. The linked dataset will be held in the secure Safe Haven for the study team to access remotely. Permission to link study survey data with DBI routine data at an individual level and to link this combined dataset to the UCD will be sought separately from the NHS Health Scotland Public Benefits and Privacy Panel and full details of all data storage, transfer and processing will be scrutinised through that process. In the previous DBI evaluation, permission was granted to link individual DBI service user evaluation survey data with routine DBI data and successfully completed and analysed. The study team are experienced in conducting data linkage studies using Public Health Scotland's Unscheduled Care Datamart.

The secure linkage of DBI data will be carried out by Public Health Scotland and will comply with all the required governance arrangements for access to such linkages. Routinely collected monitoring data will be accessed by the research team via Public Health Scotland who are collecting this data. No identifiable information will be gathered. The individual's unique number will be used to enable back tracing of data for quality purposes. The linked datasets will be stored by eDRIS in the Safe Haven for 2 years following the study. Public Health Scotland PBPP permissions will be sought for the above arrangements for access to linked datasets.

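### The comparator's unscheduled-care records are requested for 2018-2019, a window that gives no comparator person a complete outcome year after an October 2019 to March 2020 index call

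*Protocol*

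**What the plan says.** The comparator index window is fixed in section 7.1: "People who contacted NHS 24 in October 2019 to March 2020 for mental health reasons".

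Three sections give the dates of the Unscheduled Care Datamart (UCD) records wanted for these people, and all three give 2018-2019:

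- Section 5.2.4: "for 2018-2019 for people who contacted NHS 24 in October 2019 to March 2020 for mental health reasons".
- Section 7.2.1: "Unscheduled Care Datamart records for 2018-2019 for people who contacted NHS 24 in October 2019 to March 2020".
- Section 8.6, on what eDRIS will be asked to do: "link Unscheduled Care Datamart records for 2018-2019 for people who contacted NHS 24 in October 2019 to March 2020".

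Section 5.2.4 also says that the team will "collect information on service use outcomes in the year before and the year after the index call". Section 5.3 makes the frequency of unscheduled care in the year after intervention the outcome, adjusted for the preceding year. The power model in section 7.2.1 likewise takes UCD use in the year after as its dependent variable. No section asks for comparator records from 2020 or 2021 by date.

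Section 5.2.4 describes the window a second way, as use "in the year before and after the selected year for the comparator group and the data collection year for DBI service users". It also says that DBI recipients from the same period will be identified. Section 7.2.1 instead bases the sample size on people accessing DBI L2 during the study period, and section 7.3.1 sets survey recruitment at September 2022 to August 2023.

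**The concern.** The record window and the outcome window do not fit together. A call between October 2019 and March 2020 has its outcome year almost entirely in 2020 and early 2021, after the requested records end. This is the study's only quantitative comparison with people who did not receive DBI. It is the basis for the section 4 research question on whether DBI L2 is associated with a greater reduction in unscheduled care than in the historical group. Later analysis cannot recover records that were never extracted.

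A lesser inconsistency sits beside it. Section 5.2.4 defines before and after once from each person's index call and once from a calendar year, and the period that defines the DBI group is not the same throughout. The two groups therefore lack a single stated observation window.

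**Working it through.** **Inputs.** Index dates 1 October 2019 to 31 March 2020 (7.1, 5.2.4, 7.2.1). One year before and one year after each call (5.2.4). Record window 2018-2019 (5.2.4, 7.2.1, 8.6). The protocol does not say whether 2018-2019 means calendar or financial years, so three readings are tried. Each year is taken as 365 days, excluding the index day.

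**Span needed.** First call minus 365 days: 1 October 2018. Last call plus 365 days: 31 March 2021.

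**Number of index dates.** October to December 2019 has 31 + 30 + 31 = 92 dates. January to March 2020 has 31 + 29 + 31 = 91. Total 183.

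**Coverage of the outcome year.** For each index date, coverage = (days after the call that fall inside the record window) / 365.

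*Calendar years, records to 31 December 2019.*
- A call on 1 October 2019 has 91 days left in the window: 91/365 = 24.9%, the maximum.
- Covered days fall by one per date, from 91 to 0. Their sum is 91 × 92 / 2 = 4,186.
- Mean coverage = 4,186 / (183 × 365) = 4,186 / 66,795 = 6.3%.
- No coverage for calls on 31 December 2019 or later: 92/183 = 50.3% of index dates.

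*Financial year 2018/19, records to 31 March 2019.* The window closes before the first call, so coverage is 0% for every date.

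*Two financial years, records to 31 March 2020.*
- A call on 1 October 2019 has 182 days: 182/365 = 49.9%, the maximum.
- Sum of covered days = 182 × 183 / 2 = 16,653. Mean = 16,653 / 66,795 = 24.9%.

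| Reading of 2018-2019 | Outcome year covered, mean | Maximum | Index dates with a complete outcome year | Index dates with a complete prior year |
|---|---|---|---|---|
| Calendar 2018 and 2019 | 6.3% | 24.9% | 0% | 50.8% |
| Financial year 2018/19 | 0% | 0% | 0% | 0% |
| April 2018 to March 2020 | 24.9% | 49.9% | 0% | 100% |
| 1 October 2018 to 31 March 2021 | 100% | 100% | 100% | 100% |

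Taking 2018-2019 as the baseline period alone does not help. Only the third reading gives everyone a full prior year, and follow-up records would still be requested nowhere.

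**Effect on who is selected.** This depends on the route.
- If comparators are drawn from the UCD (7.2.1, 7.4) using the requested extract, then on the calendar reading the January to March 2020 calls, 91/183 = 49.7% of index dates, fall outside it and those callers could not be found.
- If they are identified through NHS 24 data and then linked (5.1, 8.2, 8.6), selection is unaffected and only the service-use records are cut short.

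**The case against.** The strongest reply is that the intention is plain. Section 5.2.4 asks for the year before and the year after in the same paragraph as the faulty dates, and 5.3 and the power model in 7.2.1 agree with it. Section 8.6 says that linkage permission will be sought separately, with full details scrutinised in that process. Section 5.3 promises a full analysis plan before the comparator group is identified. There are several chances to catch the dates before any extract is made.

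Much of this stands, and it limits what can be claimed. A reader might infer that this exact text is what the privacy panel and eDRIS will receive. The protocol does not say so. Section 8.6 describes the linkage to be requested, but the application itself is a separate document.

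A reader might also infer that the comparator would have no outcome data at all. On the calendar reading, callers from October to 30 December 2019 would have between 1 and 91 days of follow-up, and on the two-financial-year reading every caller except those on 31 March 2020 would have some. The accurate statement is that the outcome year is incomplete for everyone. Nor can it be said without qualification that half the comparator group would be lost, since that holds only on one of the two selection routes.

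The reply does not remove the contradiction. The same dates appear in three sections, including the description of the linkage, so they are not a single slip. They are also not a detail left to the analysis plan: the protocol states a specific window, and that window cannot supply its own outcome.

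**Conclusion.** The point holds as an internal contradiction in the protocol. Under each of the three readings of 2018-2019, no comparator person has a complete outcome year. Mean coverage is about 6% on calendar years, 0% on financial year 2018/19, and about 25% on April 2018 to March 2020.

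The means assume calls spread evenly over the 183 days. The maxima and the absence of any complete outcome year do not depend on that assumption. The possible loss of about half the index window is conditional on the calendar reading and on selection from the UCD extract itself.

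Followed literally, the comparison with the historical group could not be made as planned. The documents do not support saying that it will fail, because 5.2.4 shows that both years were meant and permission is still to be sought. The correction needs to be made before the data request is submitted.

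**What to change.** 1. In sections 5.2.4, 7.2.1 and 8.6, replace the 2018-2019 record period with 1 October 2018 to 31 March 2021, that is, 12 months before the first index call to 12 months after the last. If the index window moves, move these dates with it.
2. In section 5.2.4, align the sentence built on a selected year and a data collection year with the per-person year before and after the index call.
3. Reconcile section 5.2.4, where DBI recipients come from the same period as the comparator, with sections 7.2.1 and 7.3.1, which point to the study period and to recruitment from September 2022 to August 2023. Then name the DBI index date and state the matching UCD span. For illustration only: if the DBI group is the 2022-23 recruits and the index date is the first session, the span is September 2021 to August 2024. A final-session index date would end later. If the DBI group is from October 2019 to March 2020, with the index date in that window, the span is the same as the comparator's.

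The cost is wording in three sections, one aligned sentence, one decision on the DBI period and index date, and the date range in a data request not yet approved. Finding the error after extraction would mean a further request.

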7.3 Recruitment

7.3.1 Study Recruitment Process for Individuals Accessing DBI

Over a period of one year (September 2022 to August 2023), all individuals aged 16 or over who access DBI at the six participating DBI sites will be invited to participate in the study by their DBI L2 worker at their first support session. Due to Covid restrictions DBI working formats have adapted with most DBI practitioners home working and providing support via telephone, video link (although face to face is still an option). Therefore, in most cases, the study will be explained to individuals via phone or video link by the DBI L2 practitioner using the script which covers key points in the Participant Information Sheet (PIS). DBI staff will use their discretion to introduce the survey at an appropriate time or not at all depending on the individual circumstances (e.g. high distress levels, an inappropriate referral).

When introducing the evaluation, DBI practitioners will refer to the introductory text in their Recruitment Guidance which covers the key points in the Participants Information Sheet. They will also ask individuals to read the Participant Information Sheet which covers:

- The purpose of the research
- Who is carrying it out
- What is involved in taking part and that this is voluntary
- Confidentiality and information security information
- What will happen to the information they provide
- Where they can find out more
- How to make a complaint (if needed)
- How to take part
- Details of how to access the privacy notice
- A contact for further information and to notify should they wish to withdraw from the study at any time.

The PIS will include links to the study Privacy Notice and a FAQs page and a separate Sources of Support Sheet will be also be shared with every individual invited to participate.

For individuals who wish to complete their surveys online, these documents will be included in their introductory email or text. For those who prefer to complete their surveys on paper, hard copy versions will be made available at each DBI site to be handed to individuals if the DBI L2 session is face to face or sent to those accessing DBI by telephone or video link.

In the second survey, participants will be asked to provide contact details if they agree to be contacted by the survey team to participate in interviews (face to face, by telephone or video). If they do, they will be called by a member of the study team who will ask a set of brief safe screening questions to confirm eligibility and consent to be interviewed. This process is described in detail in section 7.5. As an additional step, verbal consent is also asked for and recorded at the start of the qualitative interviews.

If individuals wish to participate in the study, they will be asked to sign a DBI Participant Consent form. The process for gaining consent is described in section 7.5.

7.3.2 Recruitment of NHS 24 Mental Health Hub Service Users for Qualitative Interviews

The sample for these interviews will be gathered via Scottish lived experience networks including those linked to the National Suicide Prevention Leadership Group. We will work with the lived experience Study Advisory Group to identify a list of groups and organisations through which to reach individuals who accessed the NHS24 MHH between Oct 2019 and March 2020 to invite them to participate in a qualitative interview. Similar safe telephone screening, risk assessment and mitigation used with DBI service user participants will be employed for this group of participants with NHS24 user participants specific Qualitative Interviews Information Sheet and Consent Forms.

7.3.3 Recruitment of DBI staff to focus groups

A list of all staff will be supplied by the central DBI team. The research team will use this to identify a sample that includes a range of staff with different levels of experience who they will invite by email to participate in the staff focus groups.

7.3.4 Recruitment of GPs to the GP survey

A list of GPs operating in the study sites will be requested from DBI Central potential GP survey participants will be emailed by the study research team and invited to participate.

7.4 Sample identification

During the first data collection year, all individuals accessing DBI L2 will be invited to participate by their L2 staff members during their first DBI session, or at another appropriate time if necessary (due to their individual circumstances) as determined at the discretion of the L2 DBI staff.

Participants who have agreed to be contacted for qualitative interviews in their second survey will be identified by the research team via their responses to the surveys which will be used to determine their eligibility for interview.

A list of all staff will be supplied by the central DBI team. The research team will use this to identify a sample that includes a range of staff with different levels of experience who they will invite to participate in the staff focus groups.

Comparator group respondents will be identified from Unscheduled Care Datamart (UCD) records as those accessing NHS24 who were not referred to DBI because they accessed services prior to the roll out of DBI throughout Scotland via NHS24.

Participants for the comparator NHS 24 Mental Health Hub service users qualitative interviews will be identified by invitations distributed via Scottish mental health lived experience networks including those linked to the National Suicide Prevention Leadership Group. We will work with the lived experience Study Advisory Group to identify a list of groups and organisations through which to reach individuals who accessed the NHS24 MHH between Oct 2019 and March 2020 to invite them to participate in a qualitative interview.

A list of GPs trained in L1 DBI will be requested from DBI Central. The research team will use this list to select to take part in the GP survey.

